13. STATISTICAL ANALYSIS

Statistical analyzes will be performed in accordance with international procedures (Statistical Principles for Clinical Trials: ICH Step 4, 5 Feb 1998) and using SAS software (version 9.4).

13.1. SAMPLE SIZE

The sample size is based on the assumption that at the end of the maintenance period, 3 out of 4 patients will have at least a 20% decrease in the volume of their lymphedema in the circaid® group versus 1 in 2 in the control group. At risk alpha = 0.05, in a two-sided Chi2 test with a power of 80%, the calculation performed with Nquery (see table below) shows that the number of patients required to highlight this difference is 58 patients per group. This number is increased by 15% to account for patients lost to follow-up or unusable records, i.e. 68 per group. These patients will be recruited by 5 centers on the basis of 28 patients per center. Two group χ^2 test of equal proportions (odds ratio = 1) (equal n's)

Test significance level, α	0,050
1 or 2 sided test?	2
Group 1 proportion, π_1	0,250
Group 2 proportion, π_2	0,500
Odds ratio, $\psi = \pi_2 (1 - \pi_1) / [\pi_1 (1 - \pi_2)]$	3,000
Power (%)	80
n per group	58

13.2. PROTOCOL DEVIATIONS AND ANALYSIS PLAN

All cases of deviations from the protocol will be managed according to CEN Biotech's Standard Operating Procedures.

A detailed statistical analysis plan, based mainly on this paragraph of the study protocol, and in accordance with CEN Biotech statistical procedures, will be developed. This analysis plan will be validated by the Medical Director of medi France.

A data validation plan will first focus on defining a position when considering protocol deviations and thus define the analysis populations (Intent to Treat and Per Protocol). The analysis plan will specifically identify the statistical tests, analysis procedures, treatment of missing data considered, and the primary and secondary endpoints that will be used.

Will be considered as major deviations (patient excluded from per protocol analysis) wrong inclusions (non-compliance with the inclusion criteria and non-inclusion) and the absence of data concerning the main criterion of analysis. All other cases will be considered *a priori* as minor deviations.

13.3. ANALYZED POPULATIONS

The populations analyzed are defined as follows:

- The "Intention to treat" population (ITT) will include all patients who have applied at least once the products under study subject of this research;
- The population "per protocol" (PP) will include all patients with no major deviation from the protocol.

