4. NATURE OF THE TRIAL

Controlled randomized open label clinical trial on two parallel groups.

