9. STUDY COURSE

Following the meeting with CNEDIMTS (HAS), three observation periods were defined with the following products:

- D1 to D5: intensive hospital treatment performed by the night and day wearing of the circaid® compression system versus the night and day wearing of short stretching tapes.
- B. DD (Day of discharge from the hospital) to DD +30: ambulatory initial maintenance phase carried out by the wearing of a compression sleeve on the day associated with the nighttime compression system circaid® versus wearing a compression sleeve on the day associated with a possible treatment at night, as recommended by HAS.
- C. DD + 31 to DD + 90: ambulatory maintenance phase carried out by the wearing of a compression sleeve on the day associated with the nighttime circaid® compression system versus the wearing of a compression sleeve on the day associated with possible treatment at night.

Study design:

The study therefore includes four medical follow-up visits on day 0 (D0), day 5 (D5) (+/- 1 day), day of discharge (DD) + 30 days (+/- 5 days) and DD + 90 days (+/- 10 days), followed by self-questionnaire during the maintenance phase between DD and DD + 90, DD designating the day of discharge from the hospital at the end of the intensive reduction phase.

At D0, the doctor:

- collects the informed written consent of the patient after having duly informed her;
- collects its socio-demographic characteristics: age, occupation;
- collects the characteristics of its lymphedema: origin, date of onset, stage of edema according to the classification of the international society of lymphology, laterality of edema, volume of the arm with lymphedema, and volume of lymphedema compared to contralateral arm;

- collects the quality of life measured by the Lymph IFC specific questionnaire;
- implements decongestive treatment with the product defined by randomization.

At D5 (+/- 1 day), the doctor:

- collects the characteristics of lymphedema: stage of edema according to the classification of the international society of lymphology, volume of the arm with lymphedema, and volume of lymphedema compared to the contralateral arm;
- completes the PGII and CGII;
- records patient satisfaction in terms of efficiency and comfort of wearing measured on Likert scales in 5 classes;
- collects the occurrence of adverse events and their imputability to the products under study according to the materiovigilance;

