- collects the quality of life measured by the Lymph IFC specific questionnaire;
- gives the patient a self-questionnaire on which she reports each week who has placed the contention device (herself, spouse, nurse), and the existence of an intolerance to the wearing of it;
- gives the patient, according to the randomization list, the products under study during the maintenance phase;
- provides a nursing prescription for the application of a possible treatment to the patients concerned.

At DD + 30 days (+/- 5 days), the doctor:

- collects the characteristics of lymphedema: stage of edema according to the classification of the international society of lymphology, volume of the arm with lymphedema, and volume of lymphedema compared to the contralateral arm;
- collects the PGII and CGII;
- collects the quality of life measured by the Lymph IFC specific questionnaire;
- records patient satisfaction in terms of efficiency and wearing comfort measured on Likert scales in 5 classes;
- collects the observance of the port during the initial maintenance phase by the adapted Morisky score;
- collects the occurrence of adverse events and their imputability to the products under study according to the materiovigilance;
- retrieves the self-questionnaire from the early maintenance period and gives the patient a self-questionnaire for the maintenance period where she reports on each week who apply the compression device (herself, spouse, nurse), and the existence of an intolerance to the wearing of it;
- provides a nursing prescription for the application of a possible treatment to the patients concerned;
- gives the patient, according to the randomization list, the products under study during the maintenance phase.

At DD + 90 days (+/- 10 days), the doctor:

- collects the characteristics of lymphedema: stage of edema according to the classification of the international society of lymphology, volume of the arm with lymphedema, and volume of lymphedema compared to the contralateral arm;
- collects the PGII and CGII;
- collects the quality of life measured by the Lymph IFC specific questionnaire;

- records patient satisfaction in terms of efficiency and wearing comfort measured on Likert scales in 5 classes;
- collects the observance of the port during the long-term maintenance phase by the adapted Morisky score;
- collects the occurrence of adverse events and their imputability to the products under study according to the materiovigilance;

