13.4.2. Study of the main objective

The frequency of patients whose lymphedema volume reduction is at least 20% of the initial volume is described by numbers, frequencies, 95% confidence intervals and compared between groups by a Chi2 test at DD + 30.

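### The intention-to-treat set in 13.3 leaves out randomised patients who never apply a product, and the plan defines no all-randomised set

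*Combined protocol and SAP*

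**What the plan says.** Section 13.3 of the combined protocol and SAP defines two populations. The one called intention to treat "will include all patients who have applied at least once the products under study subject of this research". The per-protocol set "will include all patients with no major deviation from the protocol". No other population appears, neither all randomised patients nor a separate safety set.

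Section 13.2 limits major deviations to two kinds: wrong inclusions, and "the absence of data concerning the main criterion of analysis". Every other deviation counts as minor a priori. The same section defers the handling of missing outcomes: "The analysis plan will specifically identify the statistical tests, analysis procedures, treatment of missing data considered". It also says that this later plan will rest mainly on the present statistical section.

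Section 4 describes the trial as "Controlled randomized open label clinical trial on two parallel groups". Under 6.3.1 patients do or do not receive a circaid box at inclusion, according to randomisation. Under section 9 the doctor, at D0, "implements decongestive treatment with the product defined by randomization". The main criterion is "compared between groups by a Chi2 test at DD + 30" (13.4.2), with no population named.

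**The concern.** Intention to treat protects a comparison because membership is fixed by randomisation and by nothing that follows. Here membership depends on a later act, a first application, and both patient and doctor know the arm by then. A set of this kind does little harm when the decision to start cannot depend on the arm. In an open-label trial it can.

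Two things are at stake. The first is that the result could carry the ITT label although some randomised patients were removed because of how they reacted to their allocation. The second is that the two definitions do not nest: per protocol should be a subset of ITT, and as written it need not be.

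**Working it through.** **1. How the definitions classify a non-starter.** Take an eligible patient who is randomised and applies nothing.

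- ITT (13.3): out, because she has no application.
- Per protocol (13.2 with 13.3), if measured at DD+30: she is not a wrong inclusion and her main-criterion data are present, so she has no major deviation and is in.
- Per protocol, if not measured at DD+30: her main-criterion data are absent, which is a major deviation, so she is out.

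She is thus either in per protocol but not in ITT, or in neither set.

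**2. The plan's own figures.** Section 13.1 assumes 75% responders on circaid and 50% on control, two-sided alpha 0.05 and power 80%. With the pooled-variance formula, n = [1.960·√(2·0.625·0.375) + 0.842·√(0.75·0.25 + 0.50·0.50)]² / 0.25² = 57.7, rounded up to 58 per group as stated. The allowance for losses gives 58/0.85 = 68.2, against the stated 68. Section 5.3 raises the total from 136 to 140, which is 70 per arm.

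**3. Effect on one arm's rate.** Assume 70 controls with a true responder rate of 50%, so 35 responders. If k never start and would have responded with probability q, the analysed rate is (35 − kq)/(70 − k).

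| k | all would respond (q = 1) | none would respond (q = 0) |
|---|---|---|
| 1 | 34/69 = 49.3% | 35/69 = 50.7% |
| 4 | 31/66 = 47.0% | 35/66 = 53.0% |
| 7 | 28/63 = 44.4% | 35/63 = 55.6% |

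The values of k are assumptions; the documents give no rate of non-starting.

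**4. Effect on the test when there is no true difference.** Assume 68 randomised per arm, 50% response in both arms, and a fraction d of controls only who decline and are dropped. The analysed control rate is (0.50 − d·q)/(1 − d). The nominal chance of a significant result favouring circaid is 0.025. The chances below use the normal approximation to the Chi2 test.

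| d | q | apparent difference (circaid minus control) | chance of a significant result favouring circaid |
|---|---|---|---|
| 5% | 0.75 | +1.3 points | 0.035 |
| 5% | 0.25 | −1.3 points | 0.017 |
| 10% | 0.75 | +2.8 points | 0.050 |
| 10% | 0.25 | −2.8 points | 0.011 |

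At q = 0.50 there is no bias. The sign depends on the prognosis of those who decline, which cannot be known in advance.

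**5. Why counting non-starters only as non-responders is not enough.** Start from the design rates, 0.75 and 0.50. If 5% of controls do not start and are counted as non-responders, the control rate is 0.50·0.95 = 0.475 and the difference grows to 0.275. Counted as responders, it is 0.475 + 0.05 = 0.525 and the difference is 0.225. In that scenario the non-responder rule favours circaid.

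**The case against.** The strongest reply is that the route out of the ITT set is very narrow. Treatment is started by the doctor at D0, the visit at which consent and baseline data are also collected, in women who need decongestive treatment. The control bands are recommended care. Anyone who stops after a single application stays in the set. This stands, and it limits the size of the point.

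Section 14.13.3 also already asks the investigator to try to see every leaver for a final evaluation, and 13.2 promises a data validation plan that will settle the populations. The first helps and should be used. The second does not remove the problem, because the later analysis plan is to be built mainly on the text that contains this definition.

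A reader might infer three stronger claims, and the documents do not support them.

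- *Patients who finish D1 to D5 but never start maintenance are also excluded.* At D5 the doctor "gives the patient, according to the randomization list, the products under study during the maintenance phase", which might suggest that the term means the maintenance products. But section 9 also has the doctor relate adverse events at D5 to the products under study, before any maintenance product has been used. The term therefore covers the hospital phase, and these patients have already applied a product.
- *Losses will be unequal and will favour circaid.* Nothing in the documents shows unequal refusal, and the calculations run in both directions.
- *Non-starters definitely leave the primary comparison.* Section 13.4.2 names no population. That ITT is the primary set is an inference from its being intended as the broader of the two.

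**Conclusion.** The point holds as a correction of definition. The set called intention to treat is an exposed set, no all-randomised set exists, and the ITT and per-protocol definitions conflict for a patient who never starts. The likely effect is small: one non-starter among 70 controls moves the control rate by at most 0.7 points and four by at most 3.0 points, against a design difference of 25 points. These figures rest on assumed numbers of non-starters, a true control rate of 50% and losses in one arm only. The direction of any bias is unknown. The change is still worth making, because it costs little and removes a post-allocation judgement from an open-label trial.

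**What to change.** - **13.3:** define ITT as all randomised patients, analysed in the arm allocated, whatever was applied. Keep the present definition, under another name, as the set for adverse events.
- **13.4.2 and 13.4.3:** name the redefined ITT set as the population for the DD+30 primary comparison and for the DD+90 responder comparison.
- **Measurement of non-starters:** use the final evaluation already provided in 14.13.3. DD is the day of discharge after intensive reduction, so a woman who never starts may have none. State the time reference that replaces it for her.
- **Missing outcomes:** state the rule in the analysis plan. Give sensitivity results with non-starters as all responders and as all non-responders, varied by arm.

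The removal and replacement of wrong inclusions in 14.13.5 is a separate matter, but the new definition should say how it fits with that rule.

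**Cost.** The edits touch 13.3, 13.4.2, 13.4.3, the missing-data rule and one visit instruction. The planned sample size need not change. A few more patients will have missing outcomes to handle, and responder rates may be slightly lower. As an illustration, if 5% in each arm never start and all are counted as non-responders, power at 68 per arm falls from 0.862 to 0.812, still above the planned 80%. If the 5% are all in the circaid arm, it falls to 0.722.

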13.4. STATISTICAL METHODS

13.4.1. Description of the population and comparability of groups at inclusion

The sociodemographic characteristics and the characteristics of their lymphedema (origin, date of onset, stage of edema according to the classification of the international society of lymphology, laterality of the edema, volume of the arm with lymphedema, and volume of lymphedema compared to contralateral arm) will be compared between groups by Chi2 tests for qualitative variables and by Student's t-tests for quantitative variables, or their non-parametric equivalents if the characteristics of distributions require it.

13.4.2. Study of the main objective

The frequency of patients whose lymphedema volume reduction is at least 20% of the initial volume is described by numbers, frequencies, 95% confidence intervals and compared between groups by a Chi2 test at DD + 30.

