5.1. INCLUSION CRITERIA

To be included in the trial, patients will:

- be women over the age of 18;
- presenting a unilateral lymphedema of the upper limb of stage II or III according to the International Society of Lymphology, secondary to the curative ganglion treatment of a cancer, whatever its nature, and requiring a decongestive treatment by contention / compression;
- presenting an increase in the volume of the arm affected by lymphedema of at least 10% when compared to the contralateral arm;
- benefiting of the French health insurance coverage;
- duly informed of the benefits, constraints and risks of the study;
- medically and legally able to understand the methods of carrying out the study and to give written informed consent to participate in the study;
- having given their free written informed consent to their participation in the study.

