- The frequency of those who use nurses or caregivers will be described by numbers, percentages, and 95% confidence intervals and will be compared between groups by Chi2 tests or Fisher tests if the characteristics of the distributions required it. The average number of nurse visits and its standard deviation will be calculated and compared between groups by Student's t tests. Its economic impact will be quantified by mean and standard deviation and compared by Student t tests on repeated series.
- The sociodemographic and clinical factors of patients likely to influence their adhesion, their satisfaction and the maintenance of the effect on lymphedema will be studied by logistic regression analyzes in order to identify those having a significant action after adjustments on the socio-demographic and clinics characteristic of the patients.

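### The primary Chi2 test at DD+30 is valid and has its planned power, but leaves the recorded ISL stage unused; a pre-specified stage-stratified test would be a cheap safeguard

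*Combined protocol and SAP*

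**What the plan says.** - **Primary test.** Under 13.4.2 the responder frequency is described with 95% confidence intervals and "compared between groups by a Chi2 test at DD + 30". No stratum or covariate is named.
- **Eligible stages.** Section 5.1 admits "unilateral lymphedema of the upper limb of stage II or III according to the International Society of Lymphology".
- **Data at D0.** Section 9 lists ISL stage and lymphedema volume among the items the doctor collects at D0.
- **Baseline comparison.** Section 13.4.1 tests origin, date of onset, "stage of edema according to the classification of the international society of lymphology, laterality of the edema", and the volumes for differences between arms. It attaches no consequence to the result.
- **Only adjusted model.** Section 13.4.3 plans logistic regressions on "The sociodemographic and clinical factors of patients likely to influence their adhesion, their satisfaction and the maintenance of the effect on lymphedema". These look for predictors. The text names neither a treatment term nor ISL stage, and does not tie them to the DD+30 comparison.
- **Design.** Section 13.1 sizes the trial "At risk alpha = 0.05, in a two-sided Chi2 test with a power of 80" per cent, which needs 58 per group, raised to 68 for losses.
- **Still to come.** Section 13.2 says that a detailed analysis plan, based mainly on section 13, will be written and will identify the tests.

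The supplied text describes no randomisation stratified by stage.

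**The concern.** Two severity classes enter the trial, and the class is known for every patient before treatment starts. If stage II patients reach the 20% threshold more often than stage III patients, two things follow. Part of the variation in response could be removed from the comparison at no cost in patients. And if chance puts more stage III patients in one arm, the crude difference in responder rates moves against that arm, with nothing in the plan to correct it.

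The baseline tests of 13.4.1 do not fill this gap. They may show an imbalance, but the plan does not say what would then be done. The trial is open label and section 13.4.4 allows an interim analysis, so an adjustment decided after an imbalance has been seen would be easy to question. The protocol is meant to support admission to reimbursement (section 1.2), which gives that question weight.

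**Working it through.** **1. The plan's own figure.** Inputs from 13.1: "3 out of 4 patients will have at least a 20% decrease" in the circaid group "versus 1 in 2 in the control group", two-sided alpha 0.05, power 80%, equal groups. The mean rate is 0.625.

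n = [1.960 × √(2 × 0.625 × 0.375) + 0.842 × √(0.75 × 0.25 + 0.50 × 0.50)]² / 0.25²
= (1.342 + 0.557)² / 0.0625 = 57.7, so 58 per group.

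Power at 58 is Φ[(0.25 × √58 − 1.342) / 0.661] = Φ(0.85) = 80.2%. The same formula at 68 gives 86.2%. (The nQuery table prints 0.25 v 0.50, the mirror image, with the same n.) The stated size is reproduced for the unadjusted Chi2, so design and analysis match.

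**2. Assumptions.** The documents give neither the stage III share nor any link between stage and response. Assumed here: 35% stage III, a gap g in control response (stage II minus stage III) of 0 to 40 points, overall rates held at 50% and 75%, a common treatment odds ratio within stage, and 1:1 randomisation not stratified by stage.

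Control rates are 0.50 + 0.35g in stage II and 0.50 − 0.65g in stage III. At g = 0.20 they are 0.57 and 0.37, an odds ratio of (0.57 × 0.63) / (0.37 × 0.43) = 2.3. Stage then explains 0.35 × 0.65 × g² / 0.25 of the control-arm variance. This grows with the square of the gap, so small gaps yield almost nothing.

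**3. Power at 58 per arm.** In simulations of 200,000 trials per setting, Chi2 power is about 80% throughout. CMH power is 81.3%, 83.1% and 85.7% at gaps of 20, 30 and 40 points.

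| Gap (points) | Control rates II / III | Odds ratio | Variance explained | CMH minus Chi2 power (points) |
|---|---|---|---|---|
| 0 | 50% / 50% | 1 | 0% | about 0 |
| 10 | 53.5% / 43.5% | 1.5 | 0.9% | about +0.3 |
| 20 | 57% / 37% | 2.3 | 3.6% | about +1.4 |
| 30 | 60.5% / 30.5% | 3.5 | 8.2% | about +3 |
| 40 | 64% / 24% | 5.6 | 14.6% | about +6 |

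With the stage III share varied from 20% to 50%, the gain is 0.3 to 0.4 points at odds ratio 1.5, 0.8 to 1.1 at 2, 1.9 to 2.6 at 3, and 3.9 to 5.2 at 5. At 68 per arm with no stage effect, CMH is about 0.4 points below the Chi2.

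**4. How often stage is unbalanced.** The standard deviation of the difference in stage III share is √(2 × 0.35 × 0.65 / 58) = 0.0886. A gap of 15 points is 8.7 patients, so 9 or more. With a half-patient correction, 8.5 / 58 = 0.1466, and 0.1466 / 0.0886 = 1.655, a two-sided probability of about 9.8%. At 68 per arm it is about 6%.

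**5. What an imbalance does.** The crude difference shifts by imbalance × gap. At exactly 15 points this is 0.15 × 20 = 3.0, 0.15 × 30 = 4.5 and 0.15 × 40 = 6.0 points. Averaged over the trials with at least that imbalance, it is 3.7, 5.5 and 7.4 points.

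| Gap (points) | Chi2 false-positive rate, imbalance ≥ 15 points | CMH |
|---|---|---|
| 20 | about 6.5% | about 5% |
| 30 | about 8.5% | about 5% |
| 40 | about 11% | about 5% |

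Hand check at 30 points: the Chi2 rejects when the difference exceeds 1.96 × √(2 × 0.25 / 58) = 0.182. The within-stage variance is 0.65 × 0.605 × 0.395 + 0.35 × 0.305 × 0.695 = 0.2295, so the conditional standard deviation is √(2 × 0.2295 / 58) = 0.089. With a shift of 0.055 the error is Φ(−1.43) + Φ(−2.66) = 0.076 + 0.004 = 8.0%, close to the simulated value.

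Over all randomisations the Chi2 error is 5.0% to 5.1%.

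**The case against.** The strongest reply is that nothing is broken. The sample size was computed for a Chi2 and the analysis is a Chi2, so the planned 80% is delivered. The test holds its level over randomisations. **This stands.** A reader might infer from the unused stage variable that the trial loses power, or that its primary test is biased or invalid. The documents do not support either reading: at most a possible gain is not taken, and the raised error applies only conditionally, in about one trial in ten, and only if stage is prognostic.

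A second reply is that no section says stage predicts the endpoint. The endpoint is a reduction relative to the patient's own initial lymphedema volume, so an effect of severity on absolute volume need not carry over. The regressions of 13.4.3 speak of clinical factors in general and do not name stage. **This also stands**, and it is why every gain above is conditional. It does not remove the case for acting, because the possible loss (about 0.4 points) is much smaller than the possible gain.

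Third, stage is not the only candidate. Centre (5 centres in 13.1) and D0 lymphedema volume, which is the denominator of the endpoint, could also be used. **This stands** and bears on the fix: the covariates should be settled in one decision.

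Fourth, the change is more than wording. The synopsis was validated by HAS methodological experts (section 1.2), and 14.2 requires any amendment to be reported to the CPP. **This stands in part.** Under 14.2 a favourable opinion is needed only for amendments likely to modify patient safety conditions significantly, so a change of test should need reporting only.

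Last, nothing in 13.4.1 says that its tests will trigger an adjustment. That is correct. The point is that the plan does not exclude it.

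**Conclusion.** The point holds as an efficiency and robustness improvement. The primary test is unadjusted, stage is available at D0, and no rule deals with a stage imbalance in the primary comparison.

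The size depends on two quantities that the documents do not give: the stage III share and the effect of stage on response. For weak effects (odds ratio up to about 2) the power at issue is about 1 point or less. It reaches 3 to 6 points only for gaps of 30 to 40 points in control response. The protection against imbalance matters in a minority of trials, where the shift of a few points compares with a planned effect of 25 points. If stage is not prognostic, stratifying gains nothing and may cost about 0.4 points.

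This is a cheap improvement, not an error in the plan.

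**What to change.** Amend 13.4.2, and carry the same text into the analysis plan announced in 13.2, before any outcome data or interim look:

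- **Primary comparison:** CMH Chi2 test stratified by ISL stage at D0 (II v III), two-sided 5%, with the Mantel-Haenszel risk difference and its 95% confidence interval.
- **Sensitivity analysis:** the unadjusted Chi2 as now written, which keeps the link to the calculation in 13.1.
- **Fallback:** the unstratified test if a stage stratum is empty in one arm.
- **One decision on covariates:** settle stage together with centre and D0 lymphedema volume, so that a single primary test is named.
- **Selection rule:** state that the p-values of 13.4.1 do not select covariates.

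The cost is a short protocol amendment reported to the CPP, one more analysis to program, and up to about 0.4 points of power if stage is not prognostic. No new data, visits or patients are needed, and the 58 per group in 13.1 remains adequate.
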